8.1.1 Clinical Laboratory

- Hematology: total white blood cell count, hemoglobin, and platelets.
- Coagulation profile: prothrombin time (PT) and partial thromboplastin time (PTT)
- Biochemistry: sodium, potassium, glucose, blood urea nitrogen, creatinine, Cystatin c, calcium, phosphate (inorganic), uric acid, total protein, albumin, bilirubin (total), alkaline phosphatase, aspartate transaminase, alanine transaminase, gamma-glutamyl transferase, lactate dehydrogenase, and creatine phosphokinase
- Vitamin D
- Urinalysis: dipstick for presence of blood, glucose, ketones, and protein

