9. STUDY PROCEDURES AND FLOW CHART

Activity	Screening Period		Visits Treatment Period PRX-102 (Pegunigalsidase alfa)						
	Screening Visit (-3 Month)	Visit A (-2 Month) and B (-1 Month)	Visit 1	Visits 2, 4, 6, 8, 10, 12, 13, 15, 17, 19, 21, 23, 25, 26	Visits 3, 5, 9, 11	Visits 7, 20 (Months 3 and 9)	Visit 14 (Month 6)	Visits 16, 18, 22, 24	Visit 27 (Month 12)
Sign IC	x								
Assign screening number	x								
Medical history	x								
Demographics	x								
Alpha-galactosidase activity in plasma and leucocytes	x								
Historical serum creatinine	x								
Vital signs (blood pressure, pulse, temperature and respiration)	x		x	x	x	x	x	x	x
Body weight	x		x			x	x		x
Body height	x								
Physical examination	x		x			x	x		x
Concomitant medications (including pain and premedications)	x	x	x	x	x	x	x	x	x
Hematology	x		x			x	x		x
Biochemistry	x		x			x	x		x
Serum Creatinine and Cystatin C	x	x	x		x	x	x	x	x
Urinalysis - dipstick	x		x			x	x		x
Protein/Creatinine ratio spot urine test	x	x	x			x	x		x
HbsAg, HCV & HIV	x								
Serum pregnancy test (beta HCG)	x		x						

Activity	Screening Period		Visits Treatment Period PRX-102 (Pegunigalsidase alfa)						
	Screening Visit (-3 Month)	Visit A (-2 Month) and B (-1 Month)	Visit 1	Visits 2, 4, 6, 8, 10, 12, 13, 15, 17, 19, 21, 23, 25, 26	Visits 3, 5, 9, 11	Visits 7, 20 (Months 3 and 9)	Visit 14 (Month 6)	Visits 16, 18, 22, 24	Visit 27 (Month 12)
Urine Lyso Gb3 concentration	x		x			x	x		x
Plasma Lyso Gb3	x		x			x	x		x
Plasma Gb3	x		x			x	x		x
Anti PRX-102 Antibodies (IgG)			x		x	x	x		x
Electrocardiography (ECG)	x		x			x	x		x
Chest X-ray	x								
Cardiac function assessment (echocardiography and stress test)	x		x				x		x
Cardiac MRI			x						x
Inclusion/exclusion criteria	x								
Request for subject approval	x								
Enrolment approval		x ¹							
Mutation analysis			x						
PT, PTT	x								
C3, C4	x								
Vit D	x								
Short Form Brief Pain Inventory (BPI)			x			x	x		x
Brain MRI			x						x
Mainz Severity Score Index (MSSI)			x				x		x
EQ-ED-5L			x				x		x
PRX-102 infusion+clinical observation			x	x	x	x	x	x	x
Adverse event assessments		x	x	x	x	x	x	x	x

¹ After Visit B

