10.4.2 Clinical Laboratory

Summary statistics of all central and local laboratory test results (biochemistry, hematology, and urinalysis) will be presented for each visit. The change from baseline (Visit 1) to each post-treatment visit will also be presented.

If the test results were classified (e.g., low, normal, high), the frequency count and percentage will be presented for each visit, and shift table from baseline will be provided as well.

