9.2. Clinical Laboratory Test Results

The laboratory test results will be summarized, for overall and by gender, by descriptive statistics at the scheduled visits, including the change from baseline and percent change from baseline for continuous results. For the continuous test results being classified into the three categories (low, normal, high) according to the normal ranges, the shift table from baseline to each post-baseline visit will be presented as well. When available, all the test results in the following table will be summarized.

Hematology:	Biochemistry:
Hemoglobin	Alanine transaminase
Platelets	Albumin
Total white blood cell count	Alkaline phosphatase
	Aspartate transaminase
Coagulation Profile:	Bilirubin (total)
Partial thromboplastin time (PTT)	Blood urea nitrogen
Prothrombin time (PrT)	Calcium

	Creatinine
Vitamin D	Creatine phosphokinase
	Cystatin c
Urinalysis:	Gamma-glutamyl transferase
Dipstick for presence of Blood	Glucose
Dipstick for presence of Glucose	Lactate dehydrogenase
Dipstick for presence of Ketones	Phosphate (inorganic)
Dipstick for presence of Protein	Potassium
	Sodium
	Total protein
	Uric acid

Note to programmers:

- Values in urinalysis (e.g. protein), spot urine test (protein to creatinine ratio UPCR), and chemistry (e.g. bilirubin) started with a '<' sign will be excluded from the analysis, but will be presented in listings with the '<' sign.
- Serum creatinine can be recorded in two units, µmol/L and mg/dL. In calculation of eGFR or summary of creatinine, the value in µmol/L needs to be converted to mg/dL using the following conversion formula: 1 mg/dL = 88.4 µmol/L.
- Serum creatinine can be entered in two fields in the SDTM (CHEMISTRY and ENZYME). When the results from same sample is entered at both fields, then the value is identical. In such cases, only one of them will be taken in the analysis.

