14.3.1.10.2	Number of IRRs by MedDRA System Organ Class / Preferred Term by Baseline FD Classification and Treatment Emergent ADA	Safety
14.3.1.11	Number of IRRs by MedDRA System Organ Class / Preferred Term and Severity for Overall	Safety
14.3.1.12.1	Number of Subjects with IRRs by MedDRA System Organ Class / Preferred Term for Overall and by Gender	Safety

Number	Title	Population
14.3.1.12.2	Number of Subjects with IRRs by MedDRA System Organ Class / Preferred Term by Baseline FD Classification and	Safety
14.3.1.13	Number of Subjects with IRRs by MedDRA System Organ Class / Preferred Term and Severity for Overall	Safety
14.3.1.14	Treatment-Emergent Adverse Events Leading to Withdrawal or Death	Safety
14.3.1.15.1	Number of Subjects with Injection Site Reaction TEAE for Overall and by Gender	Safety
14.3.1.15.2	Number of Subjects with Injection Site Reaction TEAE by Baseline FD Classification and Treatment Emergent ADA	Safety
14.3.1.16.1	Number of Injection Site Reactions TEAE for Overall and by Gender	Safety
14.3.1.16.2	Number of Injection Site Reactions TEAE by Baseline FD Classification and Treatment Emergent ADA	Safety
14.3.1.17	Number of Subjects with Serious TEAE by MedDRA System Organ Class / Preferred Term for Overall and by Gender	Safety
14.3.1.18	Number of Subjects with Serious TEAE by MedDRA System Organ Class / Preferred Term and Relationship to Study Drug for Overall	Safety

Safety – Laboratory Test Results:

Number	Title	Population
14.3.4.1.1	Laboratory Test Results – Biochemistry for Overall and by Gender	Safety
14.3.4.1.2	Laboratory Test Results Shift from Baseline – Biochemistry for Overall and by Gender	Safety
14.3.4.2.1	Laboratory Test Results – Hematology for Overall and by Gender	Safety
14.3.4.2.2	Laboratory Test Results Shift from Baseline – Hematology for Overall and by Gender	Safety
14.3.4.3	Laboratory Test Results – Urinalysis for Overall and by Gender	Safety
14.3.4.4	Laboratory Test Results – Coagulation Profile at Screening for Overall and by Gender	Safety
14.3.4.5	Laboratory Test Results – Vitamin D at Screening for Overall and by Gender	Safety
14.3.4.6	Anti-PRX-102 Antibodies for Overall and by Gender and Baseline FD Classification	Safety

Safety – Other:

Number	Title	Population
14.3.5.1	Vital Signs for Overall and by Gender	Safety
14.3.5.2.1	Physical Examinations for Overall and by Gender	Safety
14.3.5.2.2	Physical Examinations – Shift from Baseline for Overall and by Gender	Safety

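### The SAP drops the protocol's shift table for urinalysis, so no planned summary table shows new dipstick abnormalities against each patient's baseline

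*SAP*

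**What the plan says.** **Protocol.** Section 8.1.1 defines the panel as "Urinalysis: dipstick for presence of blood, glucose, ketones, and protein". The flow chart in Section 9 (row "Urinalysis - dipstick") schedules it at Screening, Visit 1, and Visits 7, 14, 20 and 27. Section 10.4.2 brings it into the analysis: "Summary statistics of all central and local laboratory test results (biochemistry, hematology, and urinalysis) will be presented for each visit". It then adds a condition, "If the test results were classified (e.g., low, normal, high" and so on, under which counts and percentages are given per visit "and shift table from baseline will be provided as well".

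**SAP.** Section 3.2.1 lists change from baseline in clinical laboratory tests as a safety endpoint. Section 9.2 includes the dipstick results for blood, glucose, ketones and protein among the tests to be summarised. It gives change and percent change for continuous results only, and it words the shift rule in the same way: "For the continuous test results being classified into the three categories (low, normal, high) according to the normal ranges, the shift table from baseline". Section 11.1 lists "Laboratory Test Results Shift from Baseline – Biochemistry for Overall and by Gender" (Table 14.3.4.1.2) and the matching hematology table (14.3.4.2.2). For urinalysis it lists only Table 14.3.4.3, "Urinalysis for Overall and by Gender". Section 2 states that the SAP prevails where the two documents disagree.

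**The concern.** A dipstick read for the presence of a substance gives a category. The protocol's shift provision reaches categories, with low/normal/high offered only as an example, whereas the SAP's rule reaches only continuous tests. Because the SAP prevails, the narrower rule is the one that will be programmed, and the SAP gives no reason for the narrowing.

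In a single-arm switch study each patient's own baseline is the only reference. A by-visit table shows how many patients are positive at each visit. It does not show whether they are the same patients, so one who becomes positive offsets one who becomes negative. The protocol's introduction describes renal deterioration in most men and some women with Fabry disease, so a urinary finding that appears after the switch is something a safety reader would want to see in a table.

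**Working it through.** The plan states no figure to reproduce. The check is a comparison of texts, followed by simple bounds.

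**1. Which laboratory panels get a shift table?**

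| Panel | Measured after baseline? | Shift table in SAP 11.1 |
|---|---|---|
| Biochemistry | Yes | 14.3.4.1.2 |
| Hematology | Yes | 14.3.4.2.2 |
| Urinalysis (dipstick) | Yes: Visits 7, 14, 20, 27 | None; 14.3.4.3 only |
| Coagulation, vitamin D | No, screening only | Not applicable |

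Among these panels, urinalysis is the only one repeated after baseline that has no shift table.

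**2. Does the SAP avoid shift tables for categorical data in general?** No. It plans them for physical examination (9.3), qualitative ECG findings (9.4), UPCR category (10.4), the overall stress-test impression (10.6) and the EQ-5D-5L dimensions (10.9). The dipstick gap therefore looks like a by-product of the word continuous in SAP 9.2, not a policy.

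**3. What can by-visit counts tell the reader?** Let N be the number of patients with both results, a the number positive at Visit 1 and b the number positive at a later visit. From the margins of the 2×2 table alone:

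- smallest possible number of new positives = max(0, b − a)
- largest possible number of new positives = min(b, N − a)

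The documents give no dipstick counts, so every a and b below is assumed. N = 22 is the planned sample size, taken with no missing results.

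| a (assumed) | b (assumed) | Minimum | Maximum |
|---|---|---|---|
| 0 | 5 | max(0, 5) = 5 | min(5, 22) = 5 |
| 5 | 5 | max(0, 0) = 0 | min(5, 17) = 5 |
| 6 | 6 | max(0, 0) = 0 | min(6, 16) = 6 |

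If nobody is positive at baseline, the by-visit table is enough. Otherwise the number of new positives can be left open. With 5 positive at both visits, the table looks the same whether none or 5 of the 22 − 5 = 17 baseline-negative patients have converted.

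**4. What else in the plan carries the information?**

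- SAP 11.3, Listing 7.6, gives dipstick results by patient. The section allows a listing to be left out where raw-data listings are already provided and suffice.
- Table 14.2.2.9.2 shows shifts in UPCR category. It covers protein only, overall only, in the efficacy and per-protocol sets.
- Protocol 8.3.1 makes any laboratory abnormality that the investigator judges clinically significant an adverse event, so it would reach the TEAE tables.

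None of these is a summary table of dipstick change from baseline in the safety population.

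**5. A further rule affects the repair.** The programmer note in SAP 9.2 removes urinalysis values that begin with a < sign from analysis. If undetectable results are recorded that way, a change from undetectable to detectable would lose its baseline cell even in a new shift table. For UPCR, SAP 10.4 meets the same problem with a separate category for undetectable protein; the dipstick has no such category.

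**The case against.** A reader might infer that new dipstick abnormalities cannot be counted at all. The documents do not support that: with 22 planned patients and five visits (1, 7, 14, 20, 27), they can be read off Listing 7.6 or the raw-data listings. Only the summary is missing.

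A reader might also say that the protocol flatly requires a urinalysis shift table. Its wording is conditional on results being classified, and it does not say that dipstick results count as classified. The reading is natural for presence/absence data, but it is a reading. The SAP could be taken as implementing the protocol's own low/normal/high example. The SAP note on values with a < sign also suggests that some urinalysis results may be recorded as numbers.

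Much of the renal safety question is answered elsewhere: creatinine and cystatin C are in the biochemistry shift table, eGFR and its slope are analysed, UPCR has its own shift table, and clinically significant findings become adverse events. Serum glucose is also in the biochemistry panel. What remains is dipstick blood, glucose and ketones below the investigator's threshold of clinical significance.

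Finally, the table shells are in a separate document, so the layout of Table 14.3.4.3 cannot be checked. This limits certainty but does not remove the point, because the SAP text calls for no urinalysis shift and the table list names laboratory shift tables separately where they are planned.

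These arguments reduce the point to a reporting gap; they do not close it.

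**Conclusion.** The mismatch stands, and it is minor. The protocol's provision for classified laboratory results reasonably includes the dipstick, the prevailing SAP rule leaves it out, and part of a safety endpoint under the primary objective is left without a summary of change from baseline. The gap is complete in summary form for blood, glucose and ketones, and partial for protein.

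The conclusion rests on two assumptions: that dipstick results are recorded mainly as categories, and that Table 14.3.4.3 is a plain by-visit summary as the SAP text implies. The range of 0 to 5 new positives is an illustration with assumed counts, not an estimate for this trial. Nothing here suggests that the study's main safety conclusions are at risk.

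**What to change.** - In SAP 9.2, extend the shift-table sentence to categorical laboratory results, in line with Protocol 10.4.2.
- In SAP 11.1, add a dipstick shift table for blood, glucose, ketones and protein, from baseline (Visit 1, with the SAP 7.3 fallback) to Visits 7, 14, 20 and 27, in the safety population, overall and by gender.
- For this table, assign results reported with a < sign to a negative/undetectable category instead of excluding them.

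If the sponsor prefers not to add the table, the SAP should record the departure from Protocol 10.4.2 and its reason.

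The cost is one extra table from data already scheduled for collection. No protocol change and no new assessment are needed.

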11.2. Figures

Number	Title	Population
14.2.2.1.1.1	Spaghetti Plot of Plasma Lyso-Gb3 Concentrations over Time	EP
14.2.2.1.1.2	Spaghetti Plot of Plasma Lyso-Gb3 Concentrations over Time (Male Subjects)	EP
14.2.2.1.1.3	Spaghetti Plot of Plasma Lyso-Gb3 Concentrations over Time (Female Subjects)	EP

11.3. Data Listings

The following data listings would not be provided if the data listings of the raw data are already provided and suffice per sponsor’s perspective. Data listings will be sorted by the subject ID.

Number	Title
1	Subject Disposition
2	Demographics
3	Concomitant Medications
4.1	Fabry Disease Medical History
4.2	Other Medical History
5	Vital Signs
6	Physical Examination
7.1	Laboratory Test Results – Biochemistry
7.2	Laboratory Test Results – Hematology
7.3	Laboratory Test Results – Anti-PRX-102 Antibodies (IgG)
7.4	Laboratory Test Results – Gb3 Concentration (Plasma GB3 and Plasma Lyso-Gb3)
7.5	Laboratory Test Results – Spot Urine
7.6	Laboratory Test Results – Urinalysis (Dipstick)
7.7	Laboratory Test Results – Coagulation Profile
7.8	Laboratory Test Results – Vitamin D
7.9	Laboratory Test Results – GB3 Concentration (including Urine Lyso-GB3)
8	Electrocardiography (ECG)
9.1	Pre-treatment Adverse Events
9.2	Treatment Emergent Adverse Events
9.3	Fabry Clinical Events
9.4	Infusion Related Events
10	Exposure - Treatment
11.	Findings About - Brain MRI
11.	Findings About - Cardiac MRI
11.	Findings About – Stress Test
11.	Findings About - Echocardiogram
12.	Questionnaires - Brief Pain Inventory (BPI)
12.	Questionnaires – Mainz Severity Score Index (MSSI)
12.	Questionnaires – Quality of Life EQ-5D-5L
13	Protocol Deviations
14	Infusion Premedication
15	Treatment Compliance
16	X-rays
17	Pregnancies

12. TABLE SHELLS

The table shells are to be provided in a separate document.
